#### Figure 2: MCP-Mod Candidate Model Set

The significance of the dose-response signal associated with each candidate model will be determined using trend tests with model-specific optimal contrast coefficients. The maximum of the candidate model trend test statistics will be used to evaluate the presence of a dose-response signal, properly accounting for multiplicity at an overall level of 5% (1-sided) using MCP-Mod methodology. If the maximum test statistic is not significant, no dose-response relationship will be further explored. Otherwise, the model family corresponding to the candidate model with maximum trend test statistic will be used to fit to the observed data to represent the dose-response relationship. The corresponding confidence interval (CI) for the response at each dose and placebo will be computed. A bootstrap method may be used for obtaining CI as sensitivity analysis.

As a secondary analysis, age and gender will be added to the MMRM model for the MCP-MOD analyses.

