#### 1.2. Trial Design

This is a multicenter, double-blind, randomized, parallel-group, placebo-controlled, 6-week adaptive dose-finding study to assess the efficacy and safety of JNJ-42847922 as adjunctive therapy in adult subjects with MDD who have had an inadequate response to current antidepressant therapy with an SSRI/SNRI. Approximately 280 subjects will be randomized.

The doses of JNJ-42847922 that will be studied prior to the interim analysis are known (i.e., 20 and 40 mg), whereas the doses of JNJ-42847922 to be studied after the interim analysis will be adaptively chosen based on the dose-response curve observed at the interim analysis. During the interim analysis review period, subjects will continue to be randomized according to the initial randomization scheme. Regardless of whether subjects are randomized before or after the interim analysis, the schedule of events and study procedures will remain the same. The final analysis will include all subjects.

Initially, the study will assess the efficacy, dose- and exposure-response relationship, safety, and tolerability of JNJ-42847922 20 and 40 mg doses compared to placebo, when administered as adjunctive therapy to an SSRI/SNRI antidepressant. At the start of the study, subjects will be randomized in a 2:1:1 ratio to receive 1 of 3 treatments: placebo: JNJ-42847922 20 mg: JNJ-42847922 40 mg.

The data cutoff for the interim analysis will be 6 weeks after randomization of 160 subjects. An Interim Analysis Committee (IAC) will be established to review the interim data to examine the dose-response relationship and determine the doses of JNJ-42847922 and the allocation ratio of the doses to be used after the interim analysis.

After the interim analysis, subjects will be randomly assigned to study drug (placebo or 1 of the JNJ-42847922 doses [potential doses include 10 mg, 20 mg, 40 mg]), with the allocation ratio adapted according to the dose-response curve seen at the interim analysis.

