#### 1.4. Sample Size Justification

The calculation of the sample size is based on the primary efficacy endpoint (change from baseline to the end of Week 6 for the MADRS total score). The assumptions for the effect size were based on published literature and the clinically meaningful difference between groups to be detected.

The total sample size is calculated on the basis of the generalized Multiple Comparison Procedure-Modeling (MCP-Mod) test applied to the placebo and the JNJ-42847922 dose groups at the final analysis. Approximately 280 randomized subjects will provide an average weighted power of approximately 85% depending on the underlying true dose-response shape, assuming a 1-sided significance level of 0.05, a treatment difference from placebo of 4.5 points in change in MADRS total score, a standard deviation of 10, and a 25% overall dropout rate.

The data cutoff for the interim analysis will be 6 weeks after randomization of 160 subjects, which corresponds to approximately 57% of the sample size of the study. This number of subjects provides approximately 93% power to detect a dose-response relationship, depending on

the underlying true dose-response shape, assuming a treatment difference of 4.5, and a standard deviation of 10 when tested by means of the MCP-Mod approach at the 30% significance level (1-sided).

Further details regarding the interim analysis will be specified in a separate charter and interim analysis SAP.

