Subsequently, the generalized MCP-Mod approach will be applied towards the estimates obtained from the MMRM to analyze the dose-response relationship. This approach requires prespecification of a candidate model set. The actual candidate model set will depend on an interim analysis decision with two possible scenarios. The first scenario is when the 10 mg dose is not added after the interim analysis (i.e., subjects have been randomized to placebo, JNJ-42847922 20 mg and 40 mg dose groups only). For that scenario, using notation as in Bornkamp et al  $(2009)^1$ , the candidate set consists of the following 3 standardized model profiles (with the corresponding parameters): "linear" (no parameters), "emax" (ED50=1.053), and "exponential"  $(\delta = 18.20)$ . The second scenario is realized when the 10 mg dose is added after the interim analysis. For the second scenario, the candidate set is extended to the total of 4 standardized model profiles: "linear" (no parameters), "emax" (ED50=1.053), "exponential" ( $\delta$ =18.20), and "sigEmax" (ED50=14.14, h=8.496). Figure 2 below shows the extended set (of note, the maximum response is scaled to 1). Also, for the second scenario, the MCP-Mod model selection criteria will be based on the Akaike Information Criterion (AIC) with the k parameter equal to 0.5. As a sensitivity analysis, the maximum of the candidate model trend test statistics will be used as MCP-MOD model selection criterion.

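### The confidence intervals for the fitted dose-response curve take no account of model selection, and at 20 mg they under-cover for curved dose-response shapes

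*SAP*

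**What the plan says.** SAP 5.2.3.1 works in two steps. An MMRM supplies Week 6 LS means by dose group, and generalised MCP-Mod is applied to them. The dose-response test is performed "properly accounting for multiplicity at an overall level of 5% (1-sided) using MCP-Mod methodology". Only if it is significant is a curve fitted, using the family whose candidate contrast has the largest test statistic. Then: "The corresponding confidence interval (CI) for the response at each dose and placebo will be computed". The paragraph ends: "A bootstrap method may be used for obtaining CI as sensitivity analysis".

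The text before Figure 2 gives a different selection rule if the 10 mg dose is added: "the MCP-Mod model selection criteria will be based on the Akaike Information Criterion (AIC", with k = 0.5. There the maximum trend statistic is a sensitivity analysis. The text after Figure 2 names the maximum trend statistic with no such condition.

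The section mentions neither model averaging nor any other allowance for selection. A 90% level is stated for the pairwise contrasts in SAP 5.2.3.2, but no level is stated for the curve.

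**The concern.** An interval computed inside one family treats that family as fixed in advance. Here the same LS means that feed the interval also choose the family. If a straight line is chosen when the truth is curved, the interval is centred in the wrong place, and nothing in its width reflects the possibility of a wrong choice.

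Protocol 11.3 assigns MCP-Mod the task of determining the Phase 3 dose or doses, so the fitted curve and its stated precision feed that decision. With three arms, 20 mg is the only dose between the two ends of the curve, and it is the dose at which the candidate shapes differ most.

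**Working it through.** **Inputs from the documents.** 1-sided 0.05 (SAP 5.1.1). Effect 4.5 points, and "MADRS total score, a standard deviation of 10, and a 25% overall dropout rate" (SAP 1.4). Initial allocation 2:1:1 (SAP 1.2). Candidate shapes: linear, Emax with ED50 = 1.053, exponential with delta = 18.20, and sigEmax (ED50 = 14.14, h = 8.496) if 10 mg is added (SAP 5.2.3.1).

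**Assumptions not in the documents.** A 90% level and the delta method for the curve interval, the parameter bounds used in fitting, and the allocation after the interim.

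**1. The plan's own power.** Completers: 280 × 0.75 = 210, split 105 / 52.5 / 52.5. With optimal contrasts and a multivariate-t critical value, three-arm power is 84.1% (linear), 92.5% (Emax) and 81.8% (exponential). The average is (84.1 + 92.5 + 81.8)/3 = 86.1%, against the stated 85%. At the interim, 160 × 0.75 = 120 completers give 93.6%, against the stated 93%. The set-up therefore reproduces the plan.

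**2. Why the interval goes off-centre.** Scale each shape to 4.5 at 40 mg. The true effect at 20 mg is then:
- linear: 4.5 × 20/40 = 2.25
- Emax: 4.5 × (20/21.053)/(40/41.053) = 4.39
- exponential: 4.5 × (e^(20/18.20) − 1)/(e^(40/18.20) − 1) = 1.12

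Fit a straight line to the noise-free Emax means (0, 4.39, 4.50) with weights 2:1:1:
- mean dose = (0×2 + 20 + 40)/4 = 15; mean response = (4.39 + 4.50)/4 = 2.22
- slope = 134.45/1100 = 0.122; fitted value at 20 mg = 2.22 + 5 × 0.122 = 2.83
- error = 2.83 − 4.39 = −1.56
- SE of the line at 20 mg = 10 × √(1/210 + 25/(52.5 × 1100)) = 0.72; 90% half-width = 1.645 × 0.72 = 1.19

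On average the centring error exceeds the half-width. Under the exponential truth the same line gives 1.94 against 1.12, an error of +0.82. For comparison, the unmodelled 20 mg mean has SE 10/√52.5 = 1.38 and half-width 2.27.

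**3. How often this happens.** Among significant three-arm trials, the wrong family is selected in 63% (linear truth), 26% (Emax) and 36% (exponential).

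**4. Coverage at 20 mg, significant trials only.** Simulate dose-group means, apply the test, select, fit, and form the 90% delta-method interval. Three arms, 105 / 52.5 / 52.5; ranges are across independent runs:

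| Truth | Plan, response | Plan, difference from placebo | Bootstrap repeating selection, response / difference |
|---|---|---|---|
| Linear | 0.89-0.90 | 0.93 | 0.90 / 0.90 |
| Emax | 0.82-0.84 | 0.82-0.83 | 0.90 / 0.94 |
| Exponential | 0.85-0.86 | 0.83 | 0.91 / 0.91 |

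With four arms and balanced allocations assumed after the interim, AIC selection gives 0.80-0.87 and the maximum trend statistic 0.84-0.88. The bootstrap that repeats selection gives about 0.88-0.94 with four arms, from a few hundred significant trials per shape (roughly ±3 points).

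**5. Controls.**
- True family always fitted, no selection: 0.90-0.99. Selection is therefore what causes the loss.
- Bootstrap inside the already selected family: 0.76-0.80 (three arms) and 0.78-0.86 (four arms). This does not correct it.
- Placebo and 40 mg, three arms: 0.91-0.93 under the plan.
- Effect 3 instead of 4.5, three arms: 0.88-0.91. Effect 6: 0.78-0.87.

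**The case against.** **The numbers rest on assumptions.** This is correct. Level and method are not in the SAP, and the allocation after the interim is adaptive. If all later active subjects go to 10 mg, coverage at 20 mg ranges over 0.81-0.93. A reader might infer that any nominal 90% curve interval covers only 80-89%. The documents do not support so general a statement: with three arms the loss is close to zero for a linear truth or an effect of 3.

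**The optional bootstrap is not the cause.** A reader might infer that making it mandatory would cure the problem. It would not. The SAP never says that the bootstrap repeats selection, and a fixed-family bootstrap does no better than the plan. The cause is inference conditional on one selected family.

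**The intervals are not too narrow overall.** This also stands. With three arms, mean width at 20 mg is 3.74 / 4.09 / 3.95 under the plan (linear / Emax / exponential) and 3.79 / 3.76 / 3.66 for the bootstrap that repeats selection. The single-model interval is too narrow when the line is wrongly chosen, but the general fault is centring.

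**The remedy has a cost at 40 mg.** Under an Emax truth, bootstrap coverage of the response there falls from about 0.92 to about 0.86. Coverage of the difference from placebo stays at about 0.91.

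**Safeguards exist.** SAP 5.2.3.2 already plans model-free 90% intervals for each dose against placebo. The trial is described as non-confirmatory (Protocol 11.8), and in the 10 mg scenario a second selection rule is run as a sensitivity analysis. These limit the damage. They do not replace the curve interval, because SAP 5.2.3.1 presents MCP-Mod as model-based estimation in preference to pairwise testing.

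**Conclusion.** The point holds in a limited form. The single-model interval, computed as the SAP describes it, under-covers at 20 mg when the true curve is not linear: about 0.82-0.86 with three arms and about 0.80-0.87 with four arms under AIC, against an assumed 0.90. So a nominal 10% miss rate becomes roughly 13-20%. This rests on the assumed 90% delta-method interval, the SAP's planning values, conditioning on a significant test and, for four arms, an assumed allocation.

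It would be wrong to infer that the dose-response conclusion is unsafe. The primary test keeps its planned multiplicity control, and the pairwise MMRM intervals do not depend on the chosen family. What is affected is the stated precision of the fitted curve at an intermediate dose. Because that curve is meant to inform Phase 3 dose choice and the change is small, the SAP should be amended. The conflict between the AIC rule and the maximum-trend rule for the 10 mg scenario also needs resolving, although under-coverage appears under both.

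**What to change.** In SAP 5.2.3.1, replace the optional bootstrap sentence with:

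> *Two-sided 90% percentile intervals will be reported for the response at each dose and for its difference from placebo, from a parametric bootstrap of the Week 6 LS means that repeats model selection and fitting in every draw; the single-model CI will be shown alongside.*

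The bootstrap should draw from the estimated joint distribution of the LS means and take the 5th and 95th percentiles. State in the same section which selection rule, AIC with k = 0.5 or the maximum trend statistic, applies if 10 mg is added.

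The cost is one sentence, one clarification and a short program. Data collection, sample size, alpha and the primary test do not change. The loss for the absolute response at 40 mg under an Emax truth is the reason to report both intervals, and the difference from placebo, rather than drop the single-model one.

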#### 5.2.3.2. MMRM Pairwise Comparisons

In conjunction with the MCP-Mod analysis, the pairwise comparison between JNJ-42847922 doses and placebo will also be performed using the appropriate contrasts directly from the MMRM analysis described in Section 5.2.3.1, using estimates at the end of Week 6. A 90% CI for the difference in LS Means and p-value will be calculated based on the contrast test statistic for each JNJ-42847922 dose level.

As a secondary analysis, age and gender will be added to the MMRM model described in Section 5.2.3.1 for the pairwise comparison between JNJ-42847922 doses and placebo.

As a sensitivity analysis, the change in MADRS total score from baseline to the end of Week 6 will be analyzed in an MMRM analysis with the exclusion of subjects with major protocol deviations that may affect efficacy (e.g., developed withdrawal criteria but not withdrawn, entered but did not satisfy criteria, received a disallowed concomitant treatment, received wrong treatment or incorrect dose and others that may affect efficacy).

## 5.2.3.3. Sensitivity Analysis – ANCOVA with LOCF

As a sensitivity analysis, the change in MADRS total score from baseline to the end of Week 6 will be analyzed using an ANCOVA model of LOCF data. The ANCOVA model will include factors for treatment, region, baseline insomnia status (present/absent), and baseline MADRS total score as a continuous covariate. A 90% CI for the difference in LS Means and p-value will be calculated based on the contrast test statistic for each JNJ-42847922 dose level.

The last postbaseline observation during the double-blind phase will be carried forward as the "End Point (DB)". Besides the end point (DB) assessment, the LOCF values will be created for intermediate postbaseline time points as well. These imputed time points will be labeled 'Day X LOCF'.

For example, if a subject has a visit on Day 7 for the "Day 8 visit" and then a final visit on Day 10, the visit on Day 7 will be slotted to "Day 8" because Day 7 is closer to the target Day 8 than Day 10. The Day 10 visit will be used as "Day 22 LOCF", "Day 42 LOCF" and "End Point (DB)".

## 5.2.3.4. Mediation Analysis

In the mediation analysis framework, natural direct effect can be conceived of as the independent treatment effect on the outcome (i.e., change in MADRS total score) that is above and beyond its effect on the mediator (i.e., change in ISI score); controlled direct effect can be conceived of as the independent treatment effect on the outcome controlling the mediator at a fixed level; and natural indirect effect can be conceived of as a treatment effect on the outcome that is accounted for by its effect on the mediator.

A mediation analysis will be performed to examine the mediating role of improvement in sleep assessed by change from baseline in ISI score on change from baseline in MADRS total score provided that both endpoints demonstrate a statistically difference between at least one dose of JNJ-42847922 and placebo. This analysis will assess the extent to which change in MADRS total score may be mediated by or independent of change in ISI score based on observed data (i.e., data collected at each time point without carrying forward previous values) at the end of Week 6. The analysis will consider both change in MADRS total score and change in ISI score as continuous variables. The calculation of the ISI score is described in Section 5.2.3.5.

• Simulation-based Counterfactual Approach: this analysis introduced by Imai et.al  obtains the natural direct effect and natural indirect effect using numerical simulations. The approach uses parametric bootstrapping to construct the point estimate and its uncertainty estimates for direct effect and indirect effect from the bootstrap sampling distribution. For each bootstrapped sample, change from baseline in MADRS total score and change from baseline in ISI score will be analyzed. The ANCOVA analysis of change in MADRS total score from baseline will include factors for treatment (placebo and JNJ-42847922 dose groups), region, and baseline insomnia status (present/absent), change from baseline (Day 1, predose) in ISI score, treatment-by-change from baseline in ISI score as a covariate. The ANCOVA analysis of change in ISI score will include factors for treatment (placebo and JNJ-42847922 dose groups), region, and baseline MADRS total score as a covariate. The ANCOVA analysis of change in ISI score will include factors for treatment (placebo and JNJ-42847922 dose groups), region, and baseline MADRS total score as a covariate. The ANCOVA analysis of change in ISI score will include factors for treatment (placebo and JNJ-42847922 dose groups), region, and baseline insomnia status (present/absent), and baseline MADRS total score as a covariate. Estimate of the controlled direct effect will be obtained by plugging in the estimated coefficient values and the mean level of change in ISI score into the analytic expressions.

Since the relationship can be bi-directional, a mediation analysis similar to the above analysis will be performed, to assess the extent to which change in ISI score may be mediated by or independent of change in MADRS total score, based on observed data (i.e., data collected at each time point without carrying forward previous values) at the end of Week 6.

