A Multicenter, Double-Blind, Randomized, Parallel-Group, Placebo-Controlled, Adaptive Dose-Finding Study to Evaluate the Efficacy and Safety of JNJ-42847922 as Adjunctive Therapy to Antidepressants in Adult Subjects With Major Depressive Disorder Who Have Responded Inadequately to Antidepressant Therapy

JNJ-42847922 (seltorexant) is a potent and selective antagonist of the human orexin-2 receptor (OX2R, negative log of inhibition constant [pKi]=8) that is being developed for the treatment of insomnia and major depressive disorder (MDD). Preclinical evidence supports a role for the orexin system in modulating the hypothalamic-pituitary-adrenal (HPA) axis and stress-responsiveness, critical components of the pathophysiology of depression. In addition, data support the importance of attenuating sleep disturbances to attain and sustain remission in MDD, and further suggest that the sleep enhancing effects of OX2R antagonists may be of benefit to patients with MDD.

Clinical data in support of a role for orexin in depression are limited. In depressed human subjects, average cerebrospinal fluid (CSF) orexin levels have not been demonstrated to be different from controls, nor to correlate with the severity of depressive illness; however, the diurnal variation of CSF orexin levels has been shown to be blunted in subjects with depression. Data from a single dose study (42847922EDI1002) of JNJ-42847922 in a small number of subjects with MDD showed a trend towards normalization of morning cortisol levels and a reduction in depressive symptoms. The exploratory efficacy results from a multiple dose study (42847922MDD1001) of JNJ-42847922 in a small number of subjects with MDD showed an early onset (as early as Day 11 of exposure) and a clinically relevant antidepressant effect. The effect of JNJ-42847922 was largely related to an effect on the core symptoms of depression and overall unrelated to its effect on sleep-related items. The antidepressant effect was sustained at least 14 days after treatment discontinuation.

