## 5.1. Analysis Specifications

## 5.1.1. Level of Significance

The primary efficacy endpoint will be evaluated at a 1-sided significance level of 0.05 using the MCP-Mod approach to test for dose-response. For all other analyses of the primary efficacy

endpoint and for all other efficacy endpoints, no multiplicity adjustment will be done will be presented.

For the interim analysis, a 1-sided 0.30 significance level will be used to test for dose-response using the MCP-Mod approach on the change in MADRS total score to the end of Week 6. No adjustment to the final significance level will be performed due to the interim analysis.

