## 5.3.3.2. Analysis Methods

The shift in ISI score category from baseline to the end of Week 6 will be presented. A frequency distribution of the ISI individual item scores at each time point will be provided by treatment group. In addition, descriptive statistics of the ISI score at Baseline and Week 6, as well as the change from baseline to Week 6, will be presented by treatment group. Descriptive statistics will also be provided for change from baseline to the end of Week 6 in ISI total score by baseline ISI score ( $\geq$ 15 versus <15, using the randomization stratification factor as entered into IWRS)

The change in ISI score from baseline to the end of Week 6 will be analyzed using an ANCOVA model. The ANCOVA model will include factors for treatment and region, and baseline ISI score as a continuous covariate. A 90% CI for the difference in LSMeans and p-value will be calculated based on the contrast test statistic for each JNJ-42847922 dose level.

The cumulative response rate, defined as the percentage of subjects experiencing at least a given value of percent reduction from baseline to the end of Week 6 in ISI score, will be presented graphically, using observed data.

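### SAP 5.2.3.4 makes the mediation analysis wait for a significant ISI difference, so it reports nothing when ISI misses significance and, when power on ISI is low, overstates the indirect effect on average

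*SAP*

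**What the plan says.** SAP 5.2.3.4 states its purpose as assessing "the extent to which change in MADRS total score may be mediated by or independent of change in ISI score". It uses observed Week 6 data, described as "data collected at each time point without carrying forward previous values". The simulation-based method it names "obtains the natural direct effect and natural indirect effect using numerical simulations", and a controlled direct effect is added. A reverse analysis, with MADRS change as the mediator, is also planned.

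The analysis is run "provided that both endpoints demonstrate a statistically difference between at least one dose of JNJ-42847922 and placebo". The section does not say which test, level or sidedness decides this, and gives no fallback if one endpoint fails.

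The ISI result presumably comes from SAP 5.3.3.2: "The change in ISI score from baseline to the end of Week 6 will be analyzed using an ANCOVA model", with a contrast, 90% CI and p-value for each dose. SAP 5.1.1 sets the primary test: "The primary efficacy endpoint will be evaluated at a 1-sided significance level of 0.05". For everything else, "no multiplicity adjustment will be done".

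The Protocol Synopsis says the effect in the earlier multiple-dose study was largely on the "core symptoms of depression and overall unrelated to its effect on sleep-related items".

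**The concern.** An analysis meant to separate a sleep-mediated effect from a sleep-independent one runs only after a positive result on the sleep measure. Two consequences follow.

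First, a non-significant ISI result removes the direct-effect estimate and its interval. Non-significant is not the same as zero, and this is where a reader would most want to know how large a sleep-mediated component the data still allow.

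Second, the indirect effect is roughly the treatment effect on ISI multiplied by the slope of MADRS change on ISI change. Reporting it only when the first factor has passed a significance test selects trials in which that factor was overestimated.

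The stake is interpretive: how much of any antidepressant effect is attributed to sleep when the programme moves to Phase 3. The primary test is not affected.

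**Working it through.** **Inputs from the documents.** 280 randomized, 25% dropout, MADRS difference 4.5, SD 10, 1-sided 0.05 (SAP 1.4, 5.1.1); initial allocation 2:1:1 (SAP 1.2). Evaluable: 280 × 0.75 = 210, or 105 / 52.5 / 52.5 if that ratio holds throughout and 10 mg is not added.

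**Assumed, because the documents are silent.** ISI SD 5 to 6 after adjustment; true ISI effect -1.0 to -3.0, equal at both doses; ISI tested per dose at 1-sided 0.05.

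**Step 1: the plan's own power.** MCP-Mod with the three-arm candidate set of SAP 5.2.3.1 gives 84.4% (linear), 92.7% (emax) and 82.1% (exponential). The mean is 86.4%, against the stated 85% or so. The interim figure comes out at 93.7%, against about 93%. Pairwise for MADRS, SE = 10 × √(1/105 + 1/52.5) = 1.69 and power = Φ(4.5/1.69 − 1.645) = 84.6%. The inputs therefore match the plan. It states no power for ISI or for mediation.

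**Step 2: chance that the ISI condition is met.** SE = SD × √(1/105 + 1/52.5) = SD × 0.169, which is 0.845 (SD 5) or 1.014 (SD 6). The two dose contrasts share placebo, so their correlation is (1/105) / (1/105 + 1/52.5) = 1/3. The condition is met if either z-statistic exceeds 1.645 (bivariate normal).

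**Step 3: mean ISI effect once the condition is met.** Average the two dose estimates over trials that pass and divide by the truth.

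| True ISI effect | ISI condition met (SD 6 to SD 5) | Mean ISI effect inflated by (SD 5 to SD 6) |
|---|---|---|
| -1.0 | 41-50% | 51-72% |
| -1.5 | 63-75% | 18-31% |
| -2.0 | 81-91% | 6-13% |
| -3.0 | 98-100% | 0-1% |

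With no treatment-by-mediator interaction the indirect effect is proportional to the ISI effect, so it carries the same average inflation, provided the slope is not zero.

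**Step 4: both conditions simulated together.** 20,000 trials per setting; total MADRS effect 4.5; ISI SD 6; slope 0, 0.5 or 0.8 MADRS points per ISI point; no covariates or interaction.

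- *No ISI effect.* The analysis is not run in 90% of trials with a significant MADRS result (95% if tests are 2-sided). In the roughly 9% of trials where it runs, the mean indirect effect is 0.66 (slope 0.5) or 1.05 (slope 0.8), against a truth of 0.
- *ISI moves but does not drive MADRS (slope 0).* The analysis runs in 47%, 71%, 91% and 95% of trials at ISI effects of 0.2, 0.3, 0.45 and 0.6 SD. The mean direct effect is about 4.6 against 4.5, and the mean indirect effect is 0.00.
- *Real mediation.* Mean indirect effect divided by truth is 2.59 at 0.1 SD, 1.5 at 0.2, 1.19 at 0.3, 1.04 at 0.45 and 1.01 at 0.6. Individual estimates fall below the truth in 17% (0.1 SD) to about 53% (0.6 to 0.8 SD) of cases.

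The two calculations agree: -1.0 at SD 5 is 0.2 SD, with inflation of 51% in Step 3 and about 1.5-fold here.

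**Scale in MADRS points.** At 0.2 SD and slope 0.5, the true indirect effect is 0.2 × 6 × 0.5 = 0.6, or 0.6/4.5 = 13% of the total. The average reported value is 0.6 × 1.5 = 0.9, or 20%.

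**The case against.** Three stronger readings are tempting, and the documents do not support them.

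- *A reader might infer that a sleep-independent effect can never yield a direct-effect estimate.* That confuses an effect that does not run through sleep with a drug that does not change sleep. Protocol 1.1.2 reports better objective sleep in subjects with MDD, alongside an antidepressant effect largely unrelated to sleep items. In that case ISI may well reach significance, and the direct effect is then estimated.
- *A reader might infer that the indirect effect is inflated whenever it is reported.* The bias is an average. It fades as power on ISI rises and is nil when the slope is zero, and single estimates often fall below the truth.
- *A reader might work out the condition for one dose alone.* At -1.0 that gives 25-32% passing and 94-128% inflation. SAP 5.2.3.4 asks for at least one dose, which passes more often and selects less sharply.

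The best defence of the plan is that little is lost when ISI fails. With no ISI effect the indirect effect is zero and the direct effect equals the total effect, which SAP 5.2.3.2 always reports by dose with a 90% CI. The ISI contrast (5.3.3.2), MADRS-6 without the sleep item (5.3.15), MADRS by baseline ISI (5.2.3.5) and PROMIS-SD (5.3.10) are also unconditional. Mediation is not a listed objective or endpoint, and Protocol 11.8 says the trial is not confirmatory.

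Much of this stands and keeps the severity low. It does not justify the rule, because a non-significant ISI result is not a zero ISI effect. At a true -1.0, half or more of trials fail the ISI condition under these assumptions, and none of the unconditional outputs is a direct-effect estimate.

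**Conclusion.** The point holds in a limited form. The ISI condition removes the natural direct and indirect effects whenever ISI misses significance, and it biases the indirect effect upward on average when power on ISI is low. Under the stated assumptions the bias is 51-72% at a true ISI effect of -1.0 and negligible by -3.0. It does not arise if ISI change does not drive MADRS change.

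These sizes rest on an assumed ISI SD and effect, equal effects at two doses, 2:1:1 allocation throughout and a 1-sided 0.05 test. None of the ISI inputs is in the documents. The existence of the condition, its undefined test and level, and the missing fallback are plain from the SAP text.

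Minor severity: no primary inference or error rate depends on it.

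**What to change.** In SAP 5.2.3.4, delete the ISI condition. State that the analysis will be run for every JNJ-42847922 dose against placebo, with natural direct and indirect effects and their confidence intervals reported whatever the ISI p-value, and say the same for the reverse analysis. The method, as the SAP describes it, needs no significance pre-test.

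If the sponsor wants to keep some condition, it should rest on MADRS alone, with the test, level and sidedness written down. In the simulation that produces the analysis in about 95% of trials (about 90% if 2-sided), with a mean indirect effect 1.0 to 1.1 times the truth. Some selection remains, so no condition is cleaner.

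Cost: one sentence in the SAP, settled before unblinding, and at most one extra exploratory table, which is uninformative if neither endpoint moves. The primary analysis, alpha and trial conduct do not change.
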